14. Has taken NAC in the last month or experienced adverse effects/allergic reaction from it at any time
15. Significant claustrophobia and/or past negative experiences with MRI
16. Presence of non-MRI safe materials in the body (e.g., ferrous metal implants, pacemaker)

b. Source of Materials. Data collected from participants will include breathalyzer readings, urine and saliva drug screens, urine biomarkers (e.g., riboflavin), blood chemistries, plasma biomarkers, structural and neurochemical MRI brain images, cognitive testing results, and interviews and self-reports regarding substance use, psychiatric diagnoses, concomitant medications, and adverse events. To ensure confidentiality, all participant data will be number-coded, and only the investigators will have access to the master list of codes.

c. Compensation. To maximize participant retention, contingency management will be applied to participant compensation such that participants will be compensated significantly more for each subsequent MRI visit they attend (i.e., scan 1 = \$100, scan 2 = \$150), and participants will be given an additional \$50 bonus for completing both MRI visits. Participant compensation will be cash. Participants will be compensated \$50 for the initial psychiatric and medical evaluation appointment. Finally, participants will be compensated \$25 for each additional non-MRI appointment (i.e., 2 total). Compensation will thus be \$400 per participant. In our experience, this level of compensation is fair for the time commitment required without unduly coercing participants to enroll in the study despite potential concerns.

d. Potential Risks

1. Loss of Confidentiality. Individuals will be asked questions about their psychiatric symptoms. This information is highly confidential and all attempts will be made to safeguard privacy and confidentiality.
2. Medication side effects. NAC has a generally benign adverse effect profile. A meta-analysis of studies evaluating long-term oral treatment with NAC for prevention of chronic bronchitis found that NAC was well tolerated, with generally mild, most commonly gastrointestinal adverse effects that did not require treatment interruption (Grandjean et al., 2000). Common adverse effects of NAC include dry mouth, nausea, vomiting, and diarrhea. The proposed study will carefully monitor potential medication-related risks via weekly

scheduled visits and assessment of adverse events (including assessment of suicidal ideation and behavior at each and every study visit). The study physician, [name] (Co-I), will determine if the participant should be discontinued from the medication due to adverse drug reactions and will treat clinically as needed. Any confirmed incidence of serious adverse events that are deemed probably or definitely due to the study medication will result in immediate discontinuation of the study medication and follow-up assessments will be conducted until resolution. Subjects will be referred for treatment as necessary.

3. Drug interactions. Due to potential interactions with NAC, participants may not take nitroglycerin or carbamazepine at any time during participation in the study. As noted earlier, BD participants will be required to be taking a stable pre-existing regimen of at least one FDA-approved mood stabilizing medication treatment for BD. There are no known drug interactions with NAC and non-carbamazepine mood-stabilizing medications (i.e., lithium, lamotrigine, divalproex sodium, 2nd generation antipsychotic).
4. Unknown Medication Risks. While NAC is approved by the FDA, it is not approved for the use in this study (i.e. the treatment of Bipolar Disorder). Because of this, there may be unknown medication side effects. Study clinicians and the study physician will monitor all adverse events throughout the study as well as the likelihood that they are related to the study medication. In the event that there are any serious adverse events, the study physician will instruct the participant to discontinue the use of the study medication.
5. MRI-related risks. Individuals with non-MRI-safe medical implants or ferrous objects would be at risk for injury, if such individuals were allowed to enter the MRI scanner. Several precautions will be taken to ensure that individuals with ferrous implants or objects are not allowed to enter the MRI scanner. First, all potential participants will meet with a study physician to discuss any possible history of ferrous implants or other MRI-unsafe objects. Participants with any suspected history of ferrous implants or exposure to shrapnel will be excluded from the study. Second, participants who are deemed MRI-safe by the study physician will be screened for metal objects at the Center for Biomedical Imaging (CBI) using a handheld metal detector and a second metal detector built into the threshold of the doorway to the scanner. Participants who screen positive for metal will be asked to remove all metal objects from their person and will be rescreened. If participants continue to screen positive for metal after removing all metal objects from their person, they will be excluded from the study. Although not dangerous, participants who are claustrophobic could experience significant discomfort in the MRI scanner. As such, all participants will be assessed in terms of claustrophobia as well as past experience with MRI. Additionally, all participants will be entered into a “mock scanner” at the CBI human imaging center, which features the same dimensions of the real MRI scanner but without any of the internal machinery. Participants who report claustrophobia, past negative experience with MRI, or significant discomfort in the mock scanner will be excluded from participation. These procedures have been successfully used by our staff in previous and ongoing research studies of similar participant populations. For those participants allowed to participate in the MRI study, if abnormalities in collected brain images are found, participants will immediately be referred to an appropriate clinical care provider.
6. Mood destabilization. Exacerbation of depressive or manic symptoms during the course of the study is a risk for BD subjects regardless of treatment condition. We will minimize this risk by assessing mood symptoms, including suicidal ideation and behavior, at each and every study visit. Assessment of suicidal ideation will be conducted using primarily the Columbia-Suicide Severity Rating Scale (C-SSRS) and also the MADRS. Any participant who answers affirmatively to item 4 (SI with some intention of acting on them) or item 5 (SI with plan) on the C-SSRS or scoring > 4 on item 4 of the MADRS will be immediately removed from the study and procedures for emergent clinical assessment begun (see 2.c. below, *Protection Against Risk*). Participants experiencing sufficient deterioration of mood stability to result in clinically significant impairment in functional capacity will be appropriately referred. Any subject exhibiting mood destabilization that is sufficient to pose an imminent danger to self or others will be accompanied by the study physician to the University Hospital Emergency Department for immediate assessment for psychiatric hospitalization.
7. Pregnancy. MRI is used in this study. Participants who are pregnant or are trying to become pregnant should not participate as to ensure there is no risk to an embryo or fetus. Pregnancy tests will be conducted to ensure participants are not pregnant during study procedures.

2. Adequacy of Protection Against Risks

a. Recruitment and Informed Consent. Recruitment will occur by clinical referral and response to advertisements. IRB-approved study staff with advanced clinical degrees (e.g., PhD, MD) will obtain informed consent. Interested individuals will be given a brief description of the study and if still interested will be scheduled for a screening visit. At the screening visit, potential participants will be provided a copy of the IRB-approved consent document to review. After providing the participant with time to read the consent, IRB-approved study

staff will review the consent document page by page with the participant and answer any questions. Only then will the participant be asked to sign the consent document. Participants will be given a copy of the signed consent document. The entire informed consent process will be documented in the research progress notes. The signed, original consent document will be maintained in the participant source record with a copy of the consent binder located at the Institute of Psychiatry, Department of Psychiatry and Behavioral Sciences, Medical University of South Carolina.

b. Safety Assessments. At every visit, IRB-approved study staff with advanced clinical degrees (e.g., PhD, MD) will clinically evaluate subjects' manic and/or depressive symptoms, including suicidal ideation. Mood symptoms will also be quantified using standardized instruments including C-SSRS, MADRS, YMRS, BDI-II, and BAI. Adverse events will be assessed at every study visit.

c. Protection Against Risk. Psychiatric Risks. The investigative team has a great deal of experience working with the study population and has the resources to make appropriate referrals as needed. Psychiatric symptoms will be assessed on a weekly basis by standardized assessments and by clinical interview. Participants answering affirmatively to item 4 (SI with some intention of acting on them) or item 5 (SI with plan) on the C-SSRS or scoring >4 on the suicide item (item 4) of the MADRS, or otherwise exhibiting potentially life-threatening decompensation in mood or other psychiatric symptoms at any study visit will be removed from the study and procedures for emergent clinical assessment begun at once. Briefly, actively suicidal participants will be accompanied to the adult ER in the main MUSC hospital by the study psychiatrist ([name], co-I). One-to-one accompaniment and supervision by the study psychiatrist will continue until the participant is admitted for triage in the ER. Should a participant refuse voluntary assessment in the ER, MUSC Public Safety will be called immediately and involuntary commitment papers will be filled out by [name]; participants refusing voluntary assessment will be accompanied at all times by study personnel and not allowed to leave the research clinic during emergency procedures. While a rare event, over the past 15 years [name] has implemented these procedures successfully 10-12 times and study participants have been admitted to the Institute of Psychiatry without exception.

Medical Risks. NAC is largely excreted by a hepatic route. A blood chemistry panel will be performed and reviewed by the study physician prior to beginning the study medication. Participants with clinically significant hepatic (transaminases elevated > 3 times normal) insufficiency will not be eligible to participate in the study. Subjects will be referred for treatment as necessary.

MRI Risks. The investigative team has a great deal of experience with human MRI research and [name] is a core faculty member of the CBI at MUSC. MRI safety and comfort will be assessed at baseline and at each MRI visit. Participants with non-MRI-safe medical implants or ferrous objects will be excluded from participation as will individuals evidencing significant discomfort with MRI.

Pregnancy. NAC is rated as a *Category B* medication in terms of pregnancy. Because there are no adequate controlled studies of NAC in pregnant women, it is unknown whether the drug can cause fetal harm or affect reproductive capacity in humans. Therefore, women of childbearing potential must agree to pregnancy testing and use of adequate contraception in order to be eligible to participate in the study. Females will be given a urinary pregnancy test at the screening visit and weekly thereafter. Any female participant who becomes pregnant during the study will be discontinued from the study medication and removed from study participation. For all included females of childbearing potential, current forms of birth control and date of last menstruation will be assessed at each study visit.

Confidentiality. Records with identifying information (e.g., consent documents) will be stored in a locked file. All other non-MRI participant data will be collected via direct data capture (REDCap); MRI data will be automatically transferred to Linux-based servers managed by CBI. Both MRI and non-MRI data will be stored in restricted access directories on password-protected, encrypted servers managed by CBI and the Department of Psychiatry and Behavioral Sciences at MUSC. Participants will be given an ID number for all MRI and non-MRI data files. The master list of codes will be accessible only to the investigators, and will be stored in a locked office.

Emergencies. All study participants will be instructed how to access the 24-hour on-call system available at the Medical University of South Carolina. In the event that a participant experiences an adverse event after hours, s/he will be instructed to access the 24-hour on-call service. If it is determined that the participant needs immediate help, the participant may be advised to immediately go to the emergency room. In that event, proper medical treatment will be administered, per ER procedures. [name] and [name] will be available 24 hours/day, 7 days/week by pager as necessary. The Investigational Drug Service (IDS) will also be available 24 hours/day, 7 days/week for emergency identification of treatment group assignment and unblinding as

necessary.

3. Potential Benefits of the Proposed Research to the Subjects and Others

Benefits to the participants include medical and psychiatric assessments provided at no cost. Other individuals with BD are likely to benefit by the knowledge gained from the study as it may help guide future treatments

4. Importance of the Knowledge to Be Gained

Despite nearly 70 years of medication development for Bipolar Disorder (BD), BD remains one of the leading drivers of global disease burden and mortality. Existing BD medications typically leave patients with significantly impairing residual mood symptoms and cognitive dysfunction. The proposed study addresses the unmet clinical needs of BD patients using an exemplification of the modern drug discovery approach championed by the NIH and FDA: a brief, proof-of-concept study of the GSH prodrug, NAC, on neuroimaging markers of oxidative stress. Positive results may provide evidence for a novel neurobiological treatment target for BD. Such evidence would support the development and testing of medications designed to increase brain GSH levels, with potentially greater specificity and efficacy than NAC (e.g., γ -glutamylcysteine ethyl ester), using the experimental neuroimaging framework developed and validated by the proposed study. The proposed investigation's minimal risks are reasonable in relation to the importance of the knowledge to be gained from the investigation.

5. Clinicaltrials.gov Requirements

In accordance with Public Law 110-85, this project will be registered at the ClinicalTrials.gov Protocol Registration System Information Website prior to study initiation.

References

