N-acetylcysteine (NAC), a safe and well-tolerated medication, supplements endogenous GSH levels by providing cells with the rate-limiting component of GSH synthesis (i.e., cysteine) in exchange for glutamate. Though research has long demonstrated that NAC increases peripheral GSH levels, investigation of the effects of NAC on brain GSH levels has been limited to a few studies in people with Parkinson's disease and early psychosis, which found that NAC significantly increased cortical GSH levels. Based on the hypothesis that NAC treats residual BD impairments by increasing brain GSH levels, a number of randomized clinical trials (RCTs) of adjunctive NAC for BD have been conducted over the past 10-15 years. A recent meta-analysis of these RCTs found a statistically-significant, moderate effect of NAC on reducing depressive symptoms; secondary data analyses further demonstrated that NAC significantly increased working memory performance. Despite this support for NAC as a promising adjunct treatment for BD, the (GSH-mediated) mechanistic hypothesis on which these studies have been predicated has never been tested in BD individuals, and a plausible (glutamate-mediated) alternative hypothesis exists.

It is against this background that the proposed randomized, double-blind, placebo-controlled, crossover MRI study aims to measure and experimentally-increase GSH levels in dACC (selected among candidate brain regions given its central role in guiding motivated human behavior), using NAC (3g/day), in BD participants. Twelve BD participants will complete two, 2-week experimental conditions (NAC, placebo) in a randomized order, separated by a 2-week washout. The study will evaluate the following hypotheses:

Primary: NAC treatment will significantly increase dACC GSH levels, relative to placebo, in BD individuals.

Exploratory: 1) NAC treatment may significantly reduce dACC glutamate levels, relative to placebo, in BD individuals. **2)** Associations of NAC-related changes in dACC GSH and glutamate levels with peripheral biomarkers of oxidative stress (plasma GSH, s-glutathionylation), mood, and cognition will be explored.

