potential carry-over effects, conditions will be separated by a 14-day washout period, as this has been shown to prevent carry-over effects across numerous studies featuring up to 8-weeks of NAC dosing (e.g., Stav, 2009; Khaledifar, 2014). **1H-MRS Acquisition and Processing.** A structural scan will be taken for 1H-MRS voxel placement and tissue segmentation (256 sagittal slices; 1mm thick/50% gap). A dACC voxel will be placed on midsagittal T1-weighted images, posterior to the genu of the corpus callosum, with the ventral edge of the voxel aligned with the dorsal edge of the callosum (Hermann, 2012). This location was selected given its unique status as the primary hub within the network of brain structures responsible for the cognitive control of behavior (Shenhav, 2016), and because the vast majority of 1H-MRS investigations of brain GSH in psychiatric populations have acquired data from this region (Das, 2019). The voxel will be 2.5x2.5x3 cm³ to ensure adequate signal to noise properties. Following placement of 6 saturation bands 5mm away from the voxel faces and auto-shimming via FASTESTMAP, single-voxel water-suppressed 1H-MRS spectra will be acquired via TE-optimized MEGA-PRESS (TR=2000ms; TE=120ms; number of averages=256) using editing-pulse frequencies for GSH acquisition (4.56 [ON], 7.5 ppm [OFF]; Prisciandaro, 2020). See Figure 4 for representative (a) dACC voxel placement and (b) fitted data, comparing GSH spectra the TE-optimized (i.e., 120ms) acquisition (right), which provided an average of 97.3% more GSH signal, relative to the more commonly used 68-80ms TE acquisition (left). Subsequently, a low-TE PRESS sequence sensitive to glutamate will be acquired (TR=2000ms; TE=40ms; number of averages=128; Mullins, 2008). Unsuppressed water spectra will be co-acquired for each sequence. MEGA-PRESS data will be analyzed using the Gannet MATLAB toolbox (Edden, 2014). PRESS data will be analyzed using LCModel 6.3 (Provencher, 1993). Metabolites with fitting uncertainties <20% will be retained. Water will be quantified from a Gaussian-Lorentzian fit to non-water-suppressed data. Within voxel tissue fractions of gray (GM) and white (WM) matter and CSF will be calculated based on automated segmentation in Statistical Parametric Mapping 12 (Wellcome Trust) using a mask generated in Gannet. Metabolite concentrations will be normalized to unsuppressed water and corrected for within-voxel CSF fraction.

C.4. Statistical Considerations.

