C.4.a. Sample Size Determination. In the only published investigation of chronic NAC dosing on brain GSH levels in a psychiatric sample, a 23% increase in medial prefrontal GSH was found in (2.7g/day) NAC-treated participants with early psychosis, in contrast to the 4.6% decrease found in placebo-treated participants (Conus, 2018). Our test-retest investigation of TE-optimized MEGA-PRESS for Figure 2. Sample (a) dACC voxel placement (top panel), and (b) fitted GSH spectra from 80ms (left) and 120ms (right) TE MEGA-PRESS acquisitions. GSH in 11 HC demonstrated excellent stability in within-subject dACC GSH levels (*M* Coefficient of Variation = 7.25%). Using variance/covariance estimates from Prisciandaro (2020), we calculated statistical power across a range of potential magnitude between-treatment changes in dACC GSH levels. With *n*=10 study

completers ($n=12$ enrolled with an estimated dropout rate of 15-20%), the proposed study would have >80% power to detect the 23% NAC-induced increase in GSH levels reported in Conus (2018) ($\alpha=0.05$, two-tailed; IBM SPSS v27).

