C.4.b. Data Analysis. Linear mixed effects models will be used to assess the effect of NAC on dACC GSH levels (*Hypothesis 1*). Models will be re-estimated with dACC glutamate levels entered in place of GSH levels (*Exploratory Hypothesis 1*). We predict that NAC will *increase* GSH levels, but *decrease* glutamate levels, relative to placebo. *Exploratory Hypothesis 2* will be evaluated by adding the following variables, setwise, as interacting time-varying covariates to the *Hypothesis 1* linear model: i) plasma GSH levels, extent of s-glutathionylated proteins, ii) YMRS, MADRS scores, and iii) NIH Toolbox-Cognition Battery scores. Models will contain the main effect of treatment (NAC vs. placebo), period (scan 1 vs. scan 2), and sequence (NAC 1st vs. placebo 1st) to ensure the crossover design and washout were successful. Although mood-stabilizing medications have not been associated with GSH levels (Das, 2019), we will evaluate them, along with other baseline variables that may be associated with OS (age, sex, smoking status; Keaney, 2003), as moderators across analyses to facilitate rigor and reproducibility and inform future studies. Within-voxel tissue content will be evaluated as a covariate across models. We will employ previously successful methods to minimize attrition. Where missing data cannot be avoided, mixed models yield valid inferences assuming data are missing at random.

C.5. DISCUSSION

C.5.a. Overview. Despite available efficacious treatments, BD remains a leading driver of global disease burden. Convergent evidence supports ACC GSH levels as a promising interventional target, and NAC as a candidate adjunctive treatment to increase brain GSH levels, in BD individuals. The proposed randomized, placebo-controlled, double-blind, crossover MRI study aims to increase dACC GSH levels using NAC (3g/day) in individuals with BD and to evaluate medication-related, GSH- and glutamate-mediated changes in mood, cognition, and plasma biomarkers of OS, in individuals with BD. The study will be conducted by a BD research team with a successful 10+ year record of collaboration, using imaging methods optimized by the study team. Results may support the development of increasingly-targeted medications designed to fight excessive OS through increasing brain GSH levels that would clinically benefit individuals with BD.

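### Does the 20% fitting-uncertainty cut-off drop low-GSH scans in a way that distorts the NAC effect?

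*Combined protocol and SAP*

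**What the plan says.** Section C.3.c (1H-MRS Acquisition and Processing) assigns one program to each sequence. For the edited sequence that yields GSH, "MEGA-PRESS data will be analyzed using the Gannet MATLAB toolbox". For the short-echo sequence that yields glutamate, "PRESS data will be analyzed using LCModel 6.3". The next sentence is the whole retention rule: "Metabolites with fitting uncertainties <20% will be retained". It does not say what the uncertainty is, what it is a percentage of, or whether it applies to one program or both.

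Three other places bear on the point:

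- The same section describes a 2.5 x 2.5 x 3 cm voxel, 256 averages and an echo time "which provided an average of 97.3% more GSH signal" than the usual acquisition.
- Section C.4.a says that "GSH in 11 HC demonstrated excellent stability in within-subject dACC GSH levels", with a mean coefficient of variation of 7.25%. It claims more than 80% power for a 23% increase with 10 completers.
- Section C.4.b fits linear mixed models and says that "mixed models yield valid inferences assuming data are missing at random".

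**The concern.** A 20% limit reads most naturally as error divided by fitted amount. On that reading, of two scans with the same absolute noise, the one with less GSH is more likely to be rejected. The trial expects NAC to raise GSH, so if it is right, placebo scans would be rejected more often than NAC scans. Those that survive would have higher GSH than placebo scans in general, and the estimated effect would shrink. A scan removed partly because of its own unused value is not missing at random, so the statement in C.4.b does not cover it. For glutamate, where the Specific Aims say that "NAC treatment may significantly reduce dACC glutamate levels, relative to placebo, in BD individuals", the imbalance would run the other way.

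The primary endpoint rests on about 20 scans, so a few lopsided exclusions could matter. The plan has no sensitivity analysis for the rule, no count of rejections by treatment, and no allowance for rejected spectra beyond the 15 to 20% dropout.

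**Working it through.** **Inputs from the plan.** Effect 23%, coefficient of variation 7.25%, 10 completers, two-sided alpha 0.05 (all C.4.a); 20% cut-off (C.3.c). Values are put on a scale where the placebo mean is 100.

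**Assumed, because the plan gives no figure.** Between-person SD 10 or 20; fit error s lognormal with log-SD 0.2 or 0.35, independent of treatment; median s varied.

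**1. The plan's power statement.** The SD of the paired difference is √2 × 7.25 = 10.25. The standard error with 10 pairs is 10.25/√10 = 3.24, so the noncentrality is 23/3.24 = 7.1. Power exceeds 0.99 on 9 or 8 degrees of freedom. If 7.25% is the mean of two-scan coefficients of variation, the SD is larger, because the expected two-scan SD is √(2/π) = 0.798 of the true one: 7.25/0.798 = 9.1. Power is then 0.998. The stated lower bound of 80% is met either way.

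**2. The mechanism.** With relative uncertainty u = s/GSH, the same s gives a u that is 1.23 times larger on placebo than on NAC. Scans with a placebo u between 20% and 20 × 1.23 = 24.6% fail on placebo and would pass on NAC. Using the cited study's 4.6% placebo fall as well, the upper end is 20 × 1.23/0.954 = 25.8%. The imbalance is therefore real, but it acts only on scans whose error is near 20%.

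**3. How near 20% can typical errors be?** If the uncertainty is an error SD of the fitted amount, it is one component of scan-to-scan variation and cannot exceed it. A placebo scan at the mean fails when s exceeds 20 units, which is 20/7.25 = 2.8 times the reported variability (20/9.1 = 2.2 times on the two-scan reading).

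**4. Simulation with the fit error entering the measured value.** Each value is person level + effect + s × standard normal error, kept if s/value < 20%. There are 400,000 pairs per setting, and the estimate is the mean difference over complete pairs. Ranges run over the four spread settings, with a true effect of 23.

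| Median s | Implied within-person SD | Placebo lost | NAC lost | Pairs kept of 10 | Estimate |
|---|---|---|---|---|---|
| 5 | 5.2–5.7 | 0–0.2% | under 0.1% | 10.0 | 23.0 |
| 7.25 | 7.5–8.2 | 0–1.4% | 0–0.3% | 9.8–10.0 | 22.9–23.0 |
| 9.1 | 9.5–10.3 | 0.3–4.4% | 0–1.1% | 9.5–10.0 | 22.7–22.9 |
| 14 | 14.6–15.8 | 10.8–21.8% | 2.1–9.7% | 7.2–8.7 | 21.4–21.8 |
| 16 | 16.6–18.1 | 21.8–31.2% | 6.2–16.0% | 6.0–7.4 | 20.3–21.5 |

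With a true effect of 0, loss is equal in the two conditions and every estimate lies within 0.1 of zero.

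The first three rows agree with C.4.a. The last two imply within-person SDs at least twice the 7.25 reported (14.6/7.25 = 2.0).

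**5. Mixed-model check.** A likelihood fit that also uses unpaired scans, with within-person SD held at 7.25, attenuates the effect by at most 0.4% for medians of 5 to 7.25, that is 0.004 × 23 = 0.09 points. The conclusion does not depend on using complete pairs.

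**6. Power after losses.** At SD 9.1, even 8 remaining pairs give about 0.99.

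**The case for a change.** The strongest case for acting rests on the missing definition more than on the bias. Two analysts could read the sentence differently and keep different scans on the primary endpoint. Without exclusion counts by treatment, nobody could later show that the rule was harmless. The 7.25% comes from 11 healthy controls, and scans of patients may be noisier. The uncertainty might also be a residual-type measure, which the test-retest figure does not bound. A definition and one extra model run would cost little.

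Part of this stands. The term is undefined, and selection on a scan's own value does fall outside missing at random.

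The residual-type reading can be tested by holding within-person SD at 7.25 and letting the uncertainty run high without feeding it into the measured value. At a median of 16%, placebo loss is 18.0 to 31.1% against 3.0 to 14.7% on NAC, the estimate is 21.6 to 22.3, and power for 23% is still 0.95 to 0.99. If patients really were twice as noisy, power would suffer (at SD 14.5, 0.87 to 0.88 with 10 pairs and 0.75 to 0.78 with 8). Much of that would come from the noise itself, and nothing in the document indicates such noise.

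The stronger remedy, replacing the rule with criteria that ignore the metabolite level, is not clearly better. An absolute limit does equalise losses (3.7% against 3.8% at a median of 14%, within-person SD again 7.25), but it needs a reference value the plan does not contain. Taking it from healthy controls is awkward when section A.2 reports higher GSH in bipolar disorder (d = 0.66). Linewidth or signal-to-noise rules would need thresholds that are also absent.

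**Conclusion.** No change to the plan is needed. The rule is numerical, fixed in advance and the same in both conditions of a double-blind crossover. In the range that C.4.a supports, it costs at most about half a pair in 10 and 0 to 0.3 points of a 23-point effect. Any bias is toward zero, there is none when NAC has no effect, and the claim of more than 80% power holds.

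This rests on the uncertainty being an error SD of the fitted amount, on patients' scans being about as repeatable as those of the healthy controls, and on the assumed spreads. If the rule applies only to the LCModel output, which the sentence order allows although its plural subject suggests otherwise, GSH is untouched. The glutamate effect is exploratory and cannot be sized from the document.

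What is left is an undefined term. The analysts can fix its meaning for each program before unblinding, and counting rejected spectra by treatment is ordinary reporting of results.
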